6.4.3. Week 12 (± 3 days) or Early Termination

The following procedures/assessments are to be completed at this visit:

- Perform complete physical examination
- Tanner Pubertal Staging Assessment
- Vital signs
- Body weight and height
- Assessment of AEs and concomitant medications
- Pregnancy prevention counseling including partner pregnancy prevention for male participants (all subjects ≥ 12 years of age and subjects < 12 years of age at the discretion of the investigator based on subject's pubertal status)

- Subjects and parent/legal guardian will complete the relevant acceptability questionnaires.
- Quality of life survey: Subject is to review questionnaire and write/mark answers directly onto the questionnaire. Parent/legal guardian completes the parent/guardian questionnaire.
- Obtain blood samples for:
 - Hematology
 - Chemistry
 - Coagulation tests
 - HCV RNA
 - Viral sequencing (archive)
 - TSH
 - Single sparse PK sample collected anytime
 - HBV DNA testing for subjects HBcAb positive at Screening
- Obtain urine sample for:
 - Urine pregnancy test for females of childbearing potential only
- Review medication compliance with subject and/or parent/legal guardian.
- Review Subject Dosing Diary
- Subjects should return all bottles/packets of study drug at the Week 12 Visit

6.5. Posttreatment Assessments

6.5.1. 4-Week Posttreatment Visit (\pm 5 days)

The following procedures/assessments are to be completed at this site visit:

- Perform symptom-directed physical examination
- Vital signs
- Body weight and height
- Assessment of AEs and concomitant medications

- Pregnancy prevention counseling including partner pregnancy prevention for male participants (all subjects \geq 12 years of age and subjects $<$ 12 years of age at the discretion of the investigator based on subject's pubertal status)
- Obtain blood samples for:
 - Hematology
 - Chemistry
 - HCV RNA
 - Viral sequencing (archive)
 - HBV DNA testing for subjects HBcAb positive at Screening
- Obtain urine sample for:
 - Urine pregnancy test for females of childbearing potential only

6.5.2. 12-Week Posttreatment Visit (\pm 5 days)

The following procedures/assessments are to be completed at this visit:

- Perform symptom-directed physical examination
- Tanner Pubertal Stage assessment
- Vital signs
- Body weight and height
- Assessment of SAEs
- Quality of life survey: Subject is to review questionnaire and write/mark answers directly onto the questionnaire. Parent/legal guardian completes the parent/guardian questionnaire.
- Obtain blood samples for:
 - HCV RNA
 - Viral sequencing (archive)
 - HBV DNA testing for subjects HBcAb positive at Screening

6.5.3. 24-Week Posttreatment Visit (+5 days)

The following procedures/assessments are to be completed at this visit:

- Perform symptom-directed physical examination
- Tanner Pubertal Stage Assessment
- Vital signs
- Body weight and height measurements
- Assessment of SAEs
- Quality of life survey: Subject is to review questionnaire and write/mark answers directly onto the questionnaire. Parent/legal guardian completes the parent/guardian questionnaire.
- A single X-ray of the left wrist, hand, and fingers for Bone Age Assessment
- Obtain blood samples for:
 - HCV RNA
 - Viral sequencing (archive)
 - HBV DNA testing for subjects HBcAb positive at Screening

6.6.

CCI [REDACTED]

[REDACTED]

[REDACTED]

[REDACTED]

CCI
[Redacted]

[Redacted]

[Redacted]

[Redacted]

[Redacted]

[Redacted]

[Redacted]

[Redacted]

[Redacted]

[Redacted]

[Redacted]

[Redacted]

[Redacted]

[Redacted]

[Redacted]

[Redacted]

[Redacted]

[Redacted]

[Redacted]

[REDACTED]

[REDACTED]

[REDACTED]

[REDACTED]

[REDACTED]

6.7. **Unscheduled Visit**

A subject should attend an unscheduled visit if requested by the Sponsor or the investigator. The assessments are at the investigator’s discretion as clinically indicated, but the investigator should at a minimum collect AE and concomitant medication information. At all unscheduled visits initiated for the purpose of confirming virologic failure, a sample for a viral RNA sequencing/phenotyping must be collected. Unscheduled visits can be initiated to collect the sparse PK sample if not collected during the treatment visits.

6.8. **Assessments for Premature Discontinuation from Study**

If a subject discontinues study dosing (eg, as a result of an AE), every attempt should be made to keep the subject in the study and continue to perform the required study-related follow-up and procedures (see Section 3.6, Criteria for Discontinuation of Study Treatment). If this is not possible or acceptable to the subject or investigator, the subject may be withdrawn from the study.

6.9. **Breakthrough Futility Assessment**

A futility assessment will be performed after the first 10 subjects complete Week 8 on study or have viral breakthrough at or prior to Week 8. If 3 or more of the first 10 subjects enrolled have viral breakthrough at or prior to Week 8 or are non-responders (HCV RNA \geq LLOQ through 8 weeks of treatment), then further enrollment of subjects will be suspended. Virologic breakthrough is defined as confirmed HCV RNA \geq LLOQ while on treatment after two consecutive visits with HCV RNA $<$ LLOQ.

If a holding rule has been met and following an internal safety review, it is deemed appropriate to restart enrollment, a request to restart enrollment with pertinent data will be submitted to the appropriate regulatory agencies. Enrollment will only resume after review by the appropriate regulatory agencies. Any subject on treatment when a holding rule has been met will be allowed to continue to treatment.

Subjects with known or suspected study drug non-adherence will not be considered to meet the definition of virologic breakthrough, relapse, or non-responder for the purpose of this futility assessment.

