3.3. Study Treatments

3.3.1. PK Lead-in Phase

The PK Lead-in Phase will evaluate and/or confirm the age appropriate SOF/VEL FDC dose by analyzing PK, safety, and antiviral activity of SOF/VEL FDC through 7 days of dosing for each cohort. Three cohorts of at least 17 subjects each will be sequentially enrolled:

- Cohort 1: 12 to < 18 years old
- Cohort 2: 6 to < 12 years old
- Cohort 3: 3 to < 6 years old
 - At least 6 subjects weighing \geq 17 kg
 - At least 6 subjects weighing < 17 kg

[figure not shown]
The study will start with Cohort 1. Subjects will receive a SOF/VEL FDC 400/100 mg adult tablet or 2 x 200/50 mg tablets (if determined necessary based on SOF/VEL swallowability assessment) once a day for 7 days with intensive PK conducted on Day 7. If unable to swallow the tablet formulations, the subjects will receive SOF/VEL FDC 400/100 mg oral granules (8 x 50/12.5 mg packets).

Cohort 2: Subjects will receive SOF/VEL FDC 200/50 mg tablets once daily. If unable to swallow the tablet formulations, the subjects will receive SOF/VEL FDC 200/50 mg oral granules (4 x 50/12.5 mg packets).

Cohort 3: Subjects will receive SOF/VEL FDC 200/50 mg oral granules (4 x 50/12.5 mg packets) once daily for subjects weighing \geq 17 kg. SOF/VEL FDC 150/37.5 mg oral granules (3 x 50/12.5 mg packets) will be administered once daily for subjects weighing < 17 kg.

Figure 3-1. PK Lead-in Phase Study Schema

PK Lead-in

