8.6. Pharmacokinetic Analysis

PK analysis will be performed for PK Lead-in using the intensive PK Lead-in analysis set. The concentration data of VEL, SOF and metabolites (GS-566500 and GS-331007) over sampling time will be listed and summarized by nominal time and cohort. Pharmacokinetic parameters (e.g., AUC_{τ} , C_{\max} , T_{\max} , C_{last} , T_{last} , C_{τ} , and $t_{1/2}$) will be listed and summarized by cohort using descriptive statistics (eg, sample size, arithmetic mean, geometric mean, % coefficient of variation, standard deviation, median, minimum, and maximum). Plasma concentrations of the analytes over time will be plotted in semi logarithmic and linear formats as mean \pm standard deviation.

To evaluate if the exposures of SOF, GS-331007 and VEL achieved in pediatric subjects of this study are similar to the exposures observed in adult subjects, SOF, GS-331007 and VEL exposure data from this study will be compared to the integrated adult data. The primary endpoint of this analysis will be evaluated by carrying out an analysis of variance (ANOVA) for log-transformed SOF, GS-331007 and VEL AUC_{τ} . The secondary endpoints of this analysis will be the C_{\max} of SOF, VEL and GS-331007 and C_{τ} of VEL. The 90% confidence intervals will be constructed for the ratio of geometric means of each PK parameters. The equivalence boundary is set as 70% to 200%.

Dose ranging studies for SOF established that a dose of 200 mg results in suboptimal exposure compared to the 400 mg dose, and no clinically significant exposure-safety relationships were observed across a broad range of GS-331007 exposure. The Phase 1 dose ranging study GS-US-281-0102 established the anti-HCV activity of VEL and the E_{\max} models indicated that subjects will experience near maximal antiviral response (99.5% of E_{\max}) at a VEL dose of 100 mg. In the Phase 2/3 population treated with SOF/VEL FDC 400/100 mg, virologic response rates were high across all HCV genotypes and quartiles of exposure for VEL, SOF and GS-331007, including for subjects with cirrhosis, with no consistent trends in exposure-efficacy or exposure-safety relationships. Given the observed safety and efficacy profile and the lack of exposure-response across all quartiles of SOF/VEL exposure, the bounds of 70-200% support identification of a clinically relevant difference in SOF, GS-331007 or VEL exposure in the pediatric population.

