8.7. Data Monitoring Committee

An external multidisciplinary data monitoring committee (DMC) will review the progress of the study and perform interim reviews of safety data at intervals of approximately every 6 months from the first subject enrolled in order to protect subject welfare and preserve study integrity. The DMC is to provide recommendation to the sponsor whether the nature, frequency, and severity of adverse effects associated with study treatment warrant the early termination of the study in the best interests of the participants, whether the study should continue as planned, or the study should continue with modifications. The DMC may also provide recommendations as needed regarding study design, conduct, and the need for additional meetings or an alternative meeting schedule.

The DMC's specific activities will be defined by a mutually agreed upon charter, which will define the DMC's membership, conduct, and meeting schedule.

While the DMC will be asked to advise Gilead regarding future conduct of the study, including possible early study termination, Gilead retains final decision-making authority on all aspects of the study.

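### The Section 6.9 virologic hold counts only the first 10 subjects enrolled, all adolescents on 400/100 mg, so no prespecified virologic rule in the visible text can suspend enrolment on results in children under 12

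*Protocol*

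**What the plan says.** Protocol Section 6.9 fixes the timing of the check: "A futility assessment will be performed after the first 10 subjects complete Week 8 on study", or have breakthrough by then. The trigger is "If 3 or more of the first 10 subjects enrolled have viral breakthrough at or prior to Week 8 or are non-responders", and the consequence is that "then further enrollment of subjects will be suspended". Restarting requires an internal review and then regulatory review. The section does not repeat the assessment by cohort, age group or dose.

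Section 3.3.1 fixes the order of enrolment: "The study will start with Cohort 1" (12 to <18 years) and "Three cohorts of at least 17 subjects each will be sequentially enrolled". Sections 3.3.1 and 5.2 assign adolescents 400/100 mg, children of 6 to <12 years 200/50 mg, and children of 3 to <6 years 200/50 mg at 17 kg or more and 150/37.5 mg below 17 kg.

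The other controls are:
- **Opening each age group:** review of PK and safety through Day 7 (Synopsis, Section 3.3.2).
- **Cohort dose adjustment:** may be required if more than one subject has AUCtau below the adult 2.5th percentile (Section 8.6).
- **DMC:** its remit is to "perform interim reviews of safety data at intervals of approximately every 6 months" (Section 8.7). SAP Section 2 plans only DMC analyses and a final analysis.
- **Virologic stopping criteria:** these act on the individual subject's treatment (Section 3.5).

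**The concern.** The sponsor judged that Week 8 virology should be able to stop recruitment, but the rule looks only at the age group given the adult dose, for which efficacy in adults is established. The lower doses come later in the sequence and rest on exposure matching. For ages 3 to <6 in this version they rest on body-weight scaling (Section 1.3), and that section says little is known about how some of the relevant transporters and enzymes develop.

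If on-treatment response were poor in a younger group, recruitment could continue with no prespecified point at which Week 8 results must be acted on. Virologic failure also carries a risk of emergent resistance, which the trial lists as a secondary endpoint.

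**Working it through.** **Who is counted.** Cohort 1 has at least 17 subjects and enrols first. Since 10 < 17, enrolled subjects 1 to 10 are all aged 12 to <18. Children under 12 counted: 0 of about 100.

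Section 6.9 uses two phrases, the first 10 to complete Week 8 (timing) and the first 10 enrolled (count). Suppose the count followed completion. With 17 adolescents, at least 8 would have to leave before Week 8 without breakthrough (17 − 8 = 9 remaining) before a younger child could be the tenth.

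**What dose they are assigned.** Sections 3.3.1 and 5.2 give the same total in each adolescent formulation: 1 × 400/100 = 2 × 200/50 = 8 × 50/12.5 = 400/100 mg. The Synopsis lists both 8 and 4 granule packets under 12 to <18 years. These passages must be reconciled, but neither brings a child under 12 into the rule.

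**Operating characteristics.** The documents state none for the 3-of-10 rule, so there is no figure to reproduce. With p the true rate of events the rule can count, and independence between subjects:

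P(hold) = 1 − Σ C(10,k) p^k (1−p)^(10−k), summed over k = 0, 1, 2.

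For example, at p = 0.05: 1 − (0.5987 + 0.3151 + 0.0746) = 0.0115.

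| Assumed true rate p | P(hold) in one group of 10 |
|---|---|
| 1% | 0.0001 |
| 2% | 0.0009 |
| 5% | 0.0115 |
| 10% | 0.07 |
| 20% | 0.32 |
| 30% | 0.62 |
| 40% | 0.83 |
| 50% | 0.95 |

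**As written.** P(hold) depends only on the adolescent rate. At 1% in adolescents it is 0.0001, whether the rate under 12 is 5%, 30% or 100%.

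**If applied per age group.** With 1% in adolescents and 30% in both younger groups, P(at least one hold) = 1 − (1 − 0.0001) × (1 − 0.6172)² = 0.85. With 5% in all three groups, P(any hold) = 1 − (1 − 0.0115)³ = 0.034, against 0.0115 for the single look.

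**Weight strata at 3 to <6 years.** Cohort 3 guarantees at least 6 subjects in each stratum among at least 17. Because 17 − 6 = 11, the first 10 could all weigh 17 kg or more, leaving nobody on 150/37.5 mg in the count.

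**The case against.** The strongest reply is that the design bridges on exposure. One early check of the regimen plus a PK gate for each cohort is a coherent choice, and low AUCtau would warn of under-exposure before Week 8 virology could. That stands as a reason why the omission may be deliberate, but the protocol does not say so.

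Three stronger readings are tempting, and the documents do not support them.

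- **The lower doses are untested or too low.** A reader might infer this from the Section 8.6 statement that "a dose of 200 mg results in suboptimal exposure compared to the 400 mg dose". That statement concerns sofosbuvir dose-ranging studies against the 400 mg dose, not smaller children dosed to match adult exposure. Sections 1.2.2.3 and 1.3 report Cohort 2 exposures at 200/50 mg within the adult range associated with safety and efficacy. Only Cohort 3 has no PK results in this version.
- **Nobody oversees the younger children.** Antiviral activity through Day 7 is examined in every cohort (Section 3.3.1), the DMC may advise on design and conduct (Section 8.7), the sponsor may suspend enrolment at its discretion (Section 4.1), and Section 3.5 protects each child individually. What is missing is a prespecified virologic threshold tied to enrolment.
- **A per-group rule would reliably detect a weak dose.** It would not: P(hold) is 0.07 at a 10% rate and 0.32 at 20%. Posttreatment relapse never counts. Breakthrough needs two consecutive visits below LLOQ first. With scheduled samples only at Day 7/Week 1, Week 4 and Week 8, a child first suppressed at Week 4 and detectable again at Week 8 is neither a breakthrough nor a non-responder.

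The benefit in children spared is also unknown. No accrual rate is given, and enrolment would not pause while ten children reach Week 8.

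**Conclusion.** The point holds as a gap in scope. The rule counts none of the roughly 100 planned children under 12, and no other visible prespecified rule lets virologic results suspend their enrolment. The gap is sharpest at 3 to <6 years.

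This rests on the sequential enrolment described in Section 3.3.1 and on the visible text; the redacted sections and the DMC charter could contain something relevant. The probabilities assume independent subjects and hypothetical rates of countable events. No document figure suggests that rates of 30% to 50% are likely at matched exposure. The case for change is that the added protection is cheap, not that the younger children are shown to be under-dosed.

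**What to change.** In Section 6.9, apply the existing 3-of-10 assessment and restart procedure to the first 10 subjects in each age group (12 to <18, 6 to <12 and 3 to <6 years). A hold would suspend enrolment in that group and in any younger group not yet opened. Tabulate the 3 to <6 result by weight and dose stratum, so that it is clear how many subjects on 150/37.5 mg were counted. State that the rule does not count relapse. If the adolescent-only scope is intended, say so and give the reason.

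A hold in adolescents currently suspends all enrolment. If a younger group is already open, the new wording would be narrower, so the sponsor should state which scope it wants for that look.

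The cost is a short protocol edit and two further tabulations of HCV RNA already drawn at Day 7/Week 1, Week 4 and Week 8. The chance of an unnecessary pause per group is 0.0009 at a true rate of 2% and 0.0115 at 5%. No dose or individual treatment rule changes, and subjects already on treatment continue to fall under the existing provision in Section 6.9.

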3.5. Virologic Response-Based Stopping Criteria

The following on-treatment virologic response-based treatment stopping criteria will be utilized:

- Confirmed HCV RNA \geq LLOQ after 2 consecutive HCV RNA $<$ LLOQ
- Confirmed $>1 \log_{10}$ increase from nadir
- HCV RNA \geq LLOQ through 8 weeks of treatment

Confirmation should be performed as soon as possible and must occur no later than 2 weeks after an initial observation indicating virologic failure during the on-treatment phase.

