3.6. Discontinuation Criteria

The Medical Monitor should be consulted prior to subject discontinuation when medically feasible. Study medication must be discontinued in the following instances:

- Intercurrent illness that would, in the judgment of the investigator, affect assessments of clinical status to a significant degree. Following resolution of intercurrent illness, the subject may resume study dosing at the discretion of the investigator
- Unacceptable toxicity (as defined in Section 7 of the protocol) or toxicity that, in the judgment of the investigator, compromises the ability to continue study-specific procedures or is considered to not be in the subject's best interest.
- Subject noncompliance

- Pregnancy of female subject or female partner of male subject.
- Efficacy failure as defined in Section 3.5.
- Significant protocol violation that impacts subject safety
- Subject request to discontinue for any reason; it is important to determine whether the withdrawal of consent is primarily due to an AE, lack of efficacy, or other reason.
- Discontinuation of the study at the request of Gilead, regulatory agency, or an Institutional Review Board (IRB)/Independent Ethics Committee (IEC).

Subjects who meet any of the following criteria must stop treatment with SOF/VEL FDC:

- Elevation of ALT and/or AST above the upper limit of normal and $> 5x$ Day 1 or nadir, confirmed by immediate repeat testing
- Elevation of ALT $>15x$ ULN, confirmed by immediate repeat testing
- Elevation of ALT $>3x$ Day 1 and total bilirubin $>2x$ ULN, confirmed by immediate repeat testing
- Any Grade 3 or greater rash associated with constitutional symptoms
- Any Grade 4 adverse event assessed as related to administration of SOF/VEL FDC

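### Does leaving confirmed >1 log10 rebound out of the 3-of-10 enrolment hold call for a change to Protocol 6.9?

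*Protocol*

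**What the plan says.** Protocol 3.5 gives three on-treatment virologic stopping criteria:

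1. Breakthrough: confirmed HCV RNA at or above "LLOQ after 2 consecutive HCV RNA" results below LLOQ.
2. Rebound: a confirmed rise of more than 1 log10 ("increase from nadir").
3. Non-response: HCV RNA at or above LLOQ through 8 weeks.

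Confirmation "must occur no later than 2 weeks after an initial observation indicating virologic failure". Protocol 3.6 begins "Study medication must be discontinued in the following instances" and includes "Efficacy failure as defined in Section 3.5" in its list, so any of the three ends treatment for that subject. It adds: "The Medical Monitor should be consulted prior to subject discontinuation when medically feasible".

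Protocol 6.9 (Breakthrough Futility Assessment) suspends further enrolment on this condition: "If 3 or more of the first 10 subjects enrolled have viral breakthrough at or prior to Week 8 or are non-responders". It defines non-responders as in criterion 3. It defines breakthrough as confirmed HCV RNA at or above LLOQ "while on treatment after two consecutive visits with HCV RNA" below LLOQ, which matches criterion 1. Rebound is not mentioned. Subjects with known or suspected non-adherence are left out of the count.

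**The concern.** Read together, 3.5, 3.6 and 6.9 look as though they should share one definition of virologic failure. They do not: 6.9 uses two of the three criteria. A subject can fail treatment, be taken off drug for efficacy failure, and leave the hold count unchanged. The omission works in one direction only, since it can lower the count but never raise it, and so it always favours continued enrolment.

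The rule is not trivial. If it is met, enrolment of children stops and resumes only after regulatory review. If rebound were a common mode of failure in children, a count that misses it could let enrolment run on when the rule's purpose was to halt it. Section 6.9 gives no reason for the narrower definition.

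**Working it through.** **No stated figure to reproduce.** Section 6.9 gives a threshold (3 of 10) but no target failure rate, error rate or power. The check has three parts: whether an uncounted failure can occur, how much it could matter, and whether the rule is still live.

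**Can it occur?** Scheduled on-treatment HCV RNA up to Week 8 is at Day 7/Week 1, Week 4 and Week 8 (Protocol 6.3.2, 6.4.1, 6.4.2). The LLOQ is 15 IU/mL (SAP 3.6).

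| | Week 1 | Week 4 | Week 8 | 3.5 | 6.9 |
|---|---|---|---|---|---|
| (a) | 200 | <15 | 5000, confirmed | rebound | not counted |
| (b) | 200 | 5000, confirmed | off drug | rebound | depends on reading |
| (c) | <15 | <15 | 5000, confirmed | breakthrough and rebound | counted |
| (d) | 50 | 50 | 5000, confirmed | non-response and rebound | counted |

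- (a): log10(5000/15) = 2.52, so the rise from a nadir below 15 exceeds 1 log10. Only one visit below LLOQ precedes it, so it is not breakthrough. Week 4 was below LLOQ, so it is not non-response. It adds 0.
- (b): log10(5000/200) = 1.40, so it is rebound. With confirmation within two weeks, the subject stops at about Week 6, never having been below LLOQ. Whether that is non-response depends on how a period of 8 weeks of treatment is read when treatment ended sooner.
- (c) and (d): these rebounds are counted through the other two definitions.

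So the gap is real but partial: (a) is plainly uncounted, (b) is unclear, and some rebounds count anyway.

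**How much could it matter?** Let p be the true on-treatment failure rate with every failure counted. The probability of a hold is

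P(X ≥ 3) = 1 − [(1−p)^10 + 10p(1−p)^9 + 45p²(1−p)^8].

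The documents give no rebound rate, so the effect of the omission itself cannot be derived. It can be bounded. The difference between counting everything and counting as 6.9 is written cannot exceed the probability of a hold with everything counted.

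For p, take the complements of the adult SVR figures in Protocol 1.2.2.2 and 1.2.3: 99.0% gives 1%, 97.3% gives 2.7%, and above 95% gives at most 5%.

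| p | P(X ≥ 3), ceiling on the difference |
|---|---|
| 0.01 | 0.0001 |
| 0.027 | 0.0020 |
| 0.05 | 1 − (0.5987 + 0.3151 + 0.0746) = 0.0115 |
| 0.10 (assumed, not in the documents) | 1 − (0.3487 + 0.3874 + 0.1937) = 0.0702 |

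The first three rates include relapse after treatment, which neither 3.5 nor the 6.9 trigger covers. The non-adherence exclusion removes further subjects. Both make the ceilings generous. Applying adult rates to children is an assumption.

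**Is the rule still live?** The study starts with Cohort 1 (Protocol 3.3.1), which has at least 17 subjects, so the first 10 enrolled belong to it. Cohorts are sequential, and each cohort's Day 7 data inform the next cohort's dose. This protocol version already reports Cohort 2 lead-in results (1.2.2 and Table 1-2, 20 enrolled). The first 10 Cohort 1 subjects have therefore very probably passed Week 8.

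**The case for a change.** The best argument for acting is that a futility rule should be judged where the treatment does badly, not at adult success rates. Suppose 10% of children had a failure that 6.9 counts and a further 10% had rebound only. The probability of a hold would be 0.070 as written and 0.322 with rebound counted, the latter being P(X ≥ 3) at p = 0.20. With 20% rebound only it would be 0.070 against 0.617 (p = 0.30). The drafting also looks loose rather than deliberate: the non-adherence sentence in 6.9 names relapse, which the trigger does not use, and omits rebound. Settling the wording would need no new visits or samples.

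The arithmetic stands, and so does the remark about drafting. But those rebound rates appear nowhere in the documents, so the figures show sensitivity and not an expected effect. The argument would have had force before the first subjects were enrolled. Once the ten have been observed, rewording the trigger would redefine a hold rule after its data are in.

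Nor do the sections contradict each other. Sections 3.5 and 3.6 decide when one subject stops drug; 6.9 decides when enrolment pauses. Both can be followed as written, and a narrower trial-level trigger is a legitimate choice.

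**Conclusion.** The observation about the text is correct: 6.9 uses two of the three criteria in 3.5, and a subject such as (a) is stopped but not counted. The handling of a subject such as (b) is a small ambiguity that the study team can settle case by case, and the sponsor may, if it wishes, report the first-10 count under both definitions.

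No change to the plan is needed. The rule applies once and has very probably been passed. At the cited adult rates its effect on the probability of a hold is bounded by 0.01% to 1.2%. The SVR12 estimates, their confidence intervals and the safety summaries do not depend on it.

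Subjects missed by the count are not missed by the trial. Section 3.6 takes them off drug and calls for consultation with the Medical Monitor where feasible, the sponsor may suspend screening or enrolment at any site (4.1), and the DMC may advise on conduct (8.7).

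This rests on two assumptions: that on-treatment failure in children is not far above the adult complements, and that the first 10 subjects had reached Week 8 by this protocol version. The documents available do not show whether the check was run or what it found.

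### The Protocol 6.9 enrollment hold leaves out one of the three Protocol 3.5 stopping criteria (a confirmed rise of more than 1 log10 from nadir), so some early efficacy failures go uncounted

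*Protocol*

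**What the plan says.** **Protocol 3.5** gives three on-treatment virologic stopping criteria: a confirmed return to LLOQ or above after two consecutive results below it; a confirmed rise of more than 1 log10, worded as an "increase from nadir"; and HCV RNA that stays at or above LLOQ through 8 weeks. Confirmation "must occur no later than 2 weeks after an initial observation indicating virologic failure".

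**Protocol 3.6** lists, among the reasons for which drug must be discontinued, "Efficacy failure as defined in Section 3.5".

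**Protocol 6.9** (Breakthrough Futility Assessment) sets the hold: "If 3 or more of the first 10 subjects enrolled have viral breakthrough at or prior to Week 8 or are non-responders", further enrollment is suspended. Breakthrough is defined there as a confirmed result at or above LLOQ "while on treatment after two consecutive visits with HCV RNA" below LLOQ. Non-response is defined as in 3.5. The rise from nadir is not mentioned, and no reason is given for leaving it out. Once a hold is met, "Enrollment will only resume after review by the appropriate regulatory agencies". The section also says "Subjects with known or suspected study drug non-adherence will not be considered to meet the definition of virologic breakthrough, relapse, or non-responder" for this purpose.

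**SAP 6.2.1** classes a confirmed rise of more than 1 log10 from nadir (rebound) as on-treatment virologic failure, beside breakthrough and nonresponse. The SAP has no section on the futility assessment.

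**The concern.** The hold is the plan's only prespecified rule that suspends enrollment for lack of antiviral effect. It should count the events that the protocol itself treats as efficacy failure, yet it counts two of three. A subject can be taken off drug for failure under 3.5 and add nothing to the 3-of-10 count.

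If three of the first 10 subjects fail and at least one of them fails only by rebound, the count is at most 2. Enrollment is not suspended automatically, and regulatory review before restart is not triggered. Whether to pause then rests on the sponsor's general discretion over enrollment (Protocol 4.1).

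The clause that starts the assessment has the same gap. It refers to completing Week 8 or having breakthrough, and does not say how a subject stopped earlier for rebound is handled.

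**Working it through.** The plan states no operating characteristic for the 3-of-10 rule, so there is no figure to reproduce. The check is first logical, then illustrative.

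**1. Schedule.** Up to Week 8, on-treatment HCV RNA is scheduled at Week 1 (Day 7 for lead-in subjects), Week 4 and Week 8 (Protocol 6.3.2, 6.4.1, 6.4.2 and Appendix 2). Unscheduled samples are required only to confirm failure. On scheduled visits, a 6.9 breakthrough by Week 8 therefore needs results below LLOQ at both Week 1 and Week 4.

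**2. A path that no reading counts.** Week 1 below LLOQ; Week 4 at 1,000 IU/mL; confirmed.
- Size of rise: LLOQ is 15 IU/mL (SAP 3.6). With the nadir valued at 15 or less, the rise is at least log10(1000/15) = 1.82, which exceeds 1 however a below-LLOQ nadir is valued.
- Timing: the Week 4 visit window closes on Day 28 + 3 = 31. Confirmation is due within 14 days, so by Day 45. The Week 8 visit window opens on Day 56 − 3 = 53. Drug stops before the Week 8 visit.
- Breakthrough under 6.9? No, because only one visit was below LLOQ.
- Non-response? No, because the Week 1 result was below LLOQ.
- Stopped under 3.5 and 3.6? Yes.

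**3. A path not counted on a literal reading.** Week 1 at 1,000 IU/mL; Week 4 at 20,000 IU/mL; confirmed. The rise is log10(20000/1000) = 1.30. The subject was never below LLOQ, so there is no breakthrough. Treatment ended before 8 weeks, so read literally there is no non-response through 8 weeks.

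**4. A path first seen at Week 8.** At or above LLOQ at Week 1, below at Week 4, then a rise of more than 1 log10 at Week 8. Neither 6.9 definition is met. Confirmation may come after Week 8, so this is not a clean example of a stop by Week 8.

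**5. Rebounds that are counted.** Below LLOQ at Weeks 1 and 4 with a rise at Week 8 is also breakthrough. Never below LLOQ and still treated at Week 8 is also non-response.

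An enumeration of Week 1/4/8 paths confirms the pattern. It assumed a baseline of 6 log10; five levels per visit (below LLOQ, valued at 14, and 2, 3, 4 and 5 log10); hence 5 × 5 × 5 = 125 paths. All 30 paths that stop for rebound at Week 4 were uncounted, 15 of them on the literal reading in step 3. Of the rebounds at Week 8, 15 were uncounted and 14 + 3 = 17 also met non-response or breakthrough. These are counts of paths, not probabilities.

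**6. Chance of a hold.** Let p be the true rate of any 3.5 failure and s the share that is rebound only. The documents give neither, so both are assumptions.

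P(hold) = 1 − Σ(k=0..2) C(10,k) x^k (1−x)^(10−k), with x = p if all failures count and x = p(1−s) as written.

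For example, x = 0.05 gives 1 − (0.5987 + 0.3151 + 0.0746) = 0.0115.

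| p | all counted | as written, s = 25% | s = 50% | s = 75% |
|---|---|---|---|---|
| 5% | 1.2% | 0.5% | 0.2% | 0.02% |
| 10% | 7.0% | 3.4% | 1.2% | 0.2% |
| 20% | 32% | 18% | 7.0% | 1.2% |
| 40% | 83% | 62% | 32% | 7.0% |

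At p = 1% and 3%, the all-counted figures are 0.01% and 0.28%. The loss from the omission cannot exceed the all-counted figure.

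**7. Where p might lie.** Protocol 1.2.2.2 cites adult SVR12 of 97.3% and of 618/624 = 99.0%. Non-SVR12 is thus 100 − 97.3 = 2.7% and 6/624 = 1.0%. These figures include relapse and dropout, so on-treatment failure by Week 8 should be rarer still.

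**The case against.** The strongest reply is that the gap will almost never matter. At failure rates near the adult results, a hold is very unlikely under either wording. Even among adults who had failed earlier direct-acting antivirals, 1 of 69 stopped for lack of efficacy (Protocol 1.2.2.1). The rule is a single look at the first 10 subjects, all from Cohort 1, and the current protocol already reports lead-in results from Cohorts 1 and 2, so the look has probably been taken. Other safeguards exist: the Medical Monitor should be consulted before a subject discontinues, the study is open-label, expansion in each age group waits for lead-in review, and the DMC may comment on design and conduct.

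Most of this stands, and it sets the severity. It does not remove the defect. A futility rule is there for the case where children do worse than adults. The DMC's planned reviews are of safety data (Protocol 8.7), and none of the other safeguards carries the regulatory step.

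A second reply is that a lenient reader would count the never-below-LLOQ subject as a non-responder. SAP Table 3-1 also assigns Days 43 to 70 to Week 8, so a confirmation on Days 43 to 45 could be taken as a Week 8 value. That is fair for step 3. It does not rescue step 2, where the Week 1 result rules out non-response and there is only one result below LLOQ.

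**Conclusion.** The omission is real and can produce a wrong count, but it is minor. A subject below LLOQ at Week 1 only, with a confirmed rise of more than 1 log10 at Week 4, must stop drug before Week 8 and is not counted on any reading. A rebound in a subject never below LLOQ, stopped before Week 8, is not counted on a literal reading. The conclusion rests on the scheduled visits; an extra HCV RNA result could change a classification.

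Four stronger readings are tempting, and the documents do not support them:
- That every rebound escapes the count. Those that also meet breakthrough or non-response are counted.
- That the hold is likely to be missed in practice, or that all 10 subjects could fail with a count of zero. The latter is a logical extreme. The higher rates in the table are illustrations with no basis in the documents.
- That 140 IU/mL is the protocol's threshold for rebound after a below-LLOQ result. It follows only if the nadir is valued at LLOQ − 1 = 14. Protocol 8.2.2 gives that convention for summary statistics, and 3.5 does not say how such a nadir is valued.
- That patient management or the efficacy results are affected. Individual stopping under 3.5, SVR12 and the SAP failure summary do not depend on 6.9.

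**What to change.** In Protocol 6.9, count any of the first 10 subjects who meets any Protocol 3.5 criterion first observed at or before Week 8 and later confirmed, including the rise of more than 1 log10 from nadir. Name the same events in the sentence that triggers the assessment, and extend the non-adherence exclusion to rebound. It would help to state how a below-LLOQ nadir is valued. If the look has already been taken, recount the first 10 subjects on this basis and report the count.

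The cost is a short amendment to one section and, at most, a recount of 10 subjects from data already collected. No visits or samples are added. Unnecessary holds stay rare: 0.28% at a true failure rate of 3% and 1.2% at 5%. A hold pauses enrollment only: "Any subject on treatment when a holding rule has been met will be allowed to continue to treatment".
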